#### 8.2 Bristol Medication Review Model

The Model (Figure 1) integrates common themes identified through a systematic review of the literature, with a patient-centred approach[22]. The model has a clearly defined start focused on the patient's values and preferences, which continues through the review process. There is an information gathering phase which runs in parallel with an evaluation phase. The former focuses on what is being taken and why (i.e. history taking and reconciliation, assessment of adherence, rationale for treatment), and the latter on the medicines (i.e. undertreatment, overtreatment, harm). These feed through to the final decision making and implementation stage. The model was designed to emphasise patient centredness, a holistic approach, to be more in-keeping with traditional consultation structure and patient expectations, and to be flexible to accommodate differences in approach to

consulting particularly between professions. The BMR Model has received favourable feedback at medicines optimisation training delivered by [name] (co-app) to clinicians in our local area.

Figure 1. Bristol Medication Review Model

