#### 8.2.4 Clinical system templates

Clinical templates suitable for use within the two major clinical informatics systems used by GP practices (EMIS, SystmOne) will be developed. These templates will include elements which align with the BMR Model. They will also provide links to training resources and other relevant supporting materials and show automated prescribing safety indicators (e.g. describing potentially inappropriate prescribing) which have been developed for and are widely used within routine general practice [20]. Templates are widely used by practices for recording data as part of a wide range of clinical activities, so clinicians are familiar with using them (further details are provided within the Intervention Manual; 5.0 IT Template).

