#### 10.4.1 Assessment of fidelity

The BRISMED Toolkit comprises five key elements (review model, primer document, guidance documents, training materials, IT templates), and it will be possible to quantify usage of these within all the intervention sites. Implementation data for all intervention sites will be collected from several sources. Use of the training materials will be captured through login requests to the website and time spent on the website, providing us insight into which practices have accessed these materials and for how long. We will be able also to quantify use of other BRISMED Toolkit materials on the website by clinicians (e.g. downloads of primer, guidance documents, templates).

The IT templates given to intervention practices will be designed so that data recorded within the template is coded in a specific way within the clinical record (e.g. coded record identifying use of the BRISMED Toolkit). This information will then be extracted alongside other routine clinical practice data through the ORCHID network system. This will be possible in all intervention practices and not just the subset involved in the process evaluation.

Additionally, a practice-level survey will be administered to all intervention practices at the end of intervention delivery. The survey will capture information related to usage of each the five elements of the BRISMED Toolkit and the number and type of clinicians engaging with and using the intervention to support medication reviews.

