#### 11.3.2 Main analysis – primary outcome measure

Our primary outcome will be potentially inappropriate prescribing (PIP). This will be a binary variable, including the widely used STOPP/START indicators (these are originally designed for assessing prescribing in the elderly, but many are still relevant to younger patients) and the most frequently occurring age-independent PIP indicators identified from our IMPPP trial. The potentially inappropriate prescribing indicators used in the IMPPP trial are well established and were previously successfully employed in the DQIP trial[21].

The primary analysis will use random effects Poisson regression on the practice scale to explore the rates of potentially inappropriate prescribing indicators within each GP practice at the end of the intervention period by arm using the ITT principle. The random effect will account for clustering by PCN. The number of patients potentially eligible for review at each GP site will be used as the offset term whilst also adjusting for the baseline rates of the outcome. We will determine baseline rates by looking at the electronic prescribing records at each GP site in the 12 months prior to randomisation. This will be a test for superiority focussing on the estimate, 95% CI and p-value from the regression model.

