#### 11.3.3 Secondary analyses

Analysis of the secondary outcomes will use the same method as for the primary outcome analysis. Subgroup analyses will be undertaken by age, sex, socioeconomic status, medication count, and evidence of implementation within practices (coded record identifying BMR Model). We will not fit different regression models for each subgroup, but instead will add an interaction term to the analysis model to derive the effect size within subgroups; this is more efficient and allows a hypothesis test of effect sizes being different in subgroups.

We will explore analyses on the individual level for the primary and some of the medication-related secondary analyses (e.g. medication count, MRCI). However, this approach is logistically problematic for the analysis of outcomes such as health service utilisation or medication adherence, which might take up to 12 months to become apparent. A considerable (i.e. 12-month) wait would be required after the intervention period ends for all the necessary data to become available. Analysis on the practice scale mitigates this issue.

Our analysis of quality of life and patient experience will be random effects regression models (linear, logistic or Poisson models, as appropriate) for each individual by arm using the ITT principle. A random effect will account for clustering by GP practice. This will be a test for superiority focussing on the estimate, 95% CI and p-value from the regression model.

Missing data is unlikely to be a significant issue for our main analyses, e.g. if a drug or disease is missing in routine data it is generally assumed that this corresponds to its absence rather than a recording omission, and it is generally difficult (and often impossible) to distinguish these two possibilities. Given the nature of routine health record data, other key factors such as age and gender are unlikely to be missing. We will explore the nature of missingness for other patient-level data such as ethnicity and socioeconomic deprivation, and use established approaches such as multiple imputation to address missingness if appropriate.

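### Treating an unrecorded disease or drug as absent is safe for the primary comparison only if recording stays similar in both arms; the recording template goes to one arm, and the protocol plans no check

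*Protocol*

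**What the plan says.** **Outcome.** The primary outcome is the proportion of patients in each practice who trigger at least one PIP criterion at 12 months (section 4.2.1). It is a binary variable "including the widely used STOPP/START indicators" and further age-independent indicators (section 11.3.2), derived from routine primary care records through ORCHID (sections 4.2.3 and 7.2).

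**Missing records.** Section 11.3.3 considers missing data unlikely to be a significant issue for the main analyses. Its reason is that "if a drug or disease is missing in routine data it is generally assumed that this corresponds to its absence", and it concedes that "it is generally difficult (and often impossible) to distinguish these two possibilities".

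**What the intervention arm receives.**
- Section 8.1 lists templates for recording data in the GP system among the toolkit's components.
- Section 8.2.4 says "These templates will include elements which align with the BMR Model". Section 8.2 describes that model's information-gathering phase as "history taking and reconciliation, assessment of adherence, rationale for treatment".
- Section 10.4.1 says "The IT templates given to intervention practices will be designed so that data recorded within the template is coded" in a specific way in the clinical record.
- Section 8.3 restricts the website, through which the templates are supplied, to intervention practices.

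**Adjustment.** The primary model adjusts for each practice's PIP rate in the 12 months before randomisation (section 11.3.2).

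**The concern.** Reading no record as no disease misclassifies some patients. If the misclassification is about the same in both arms, it blurs the outcome without creating a difference. If recording changes in one arm only, it can create a difference or hide one.

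Here the intervention may act on the same record from which the outcome is read. A review that works through reconciliation and the reason for each drug, entered in a coding template, could lead to diagnoses or indications being recorded that were not recorded before. Where an indicator includes a disease condition, a newly recorded diagnosis could bring a patient within it, and a newly recorded indication could take a patient out. In either case recorded PIP moves although prescribing has not.

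Randomisation and intention-to-treat analysis do not guard against this, because the change would start after allocation. Baseline adjustment does not either, because it uses records from before the template existed. At stake is whether a difference in the primary outcome, or its absence, can be attributed to prescribing.

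**Working it through.** **Inputs (section 11.1):** 250 PCNs per arm; mean size 20593, SD 15229; 40% eligible; ICC 0.04; control rate 20%; 15% relative reduction, so 17% in the intervention arm; alpha 5%, taken as two-sided.

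**Step 1. Reproduce the plan's power.**
- Eligible patients per PCN: m = 0.40 × 20593 = 8237.
- Coefficient of variation: CV = 15229 / 20593 = 0.7395; CV² = 0.547.
- Design effect: 1 + [(1 + CV²) × m − 1] × ICC = 1 + (12742 − 1) × 0.04 = 510.6.
- Effective patients per arm: 250 × 8237 / 510.6 ≈ 4033.
- Two-proportion z test, 0.20 against 0.17: power 93.5%. The protocol states 93.3%, so the figure reproduces.

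**Step 2. Scale of a recording shift.** With both arms at 20%, the standard error of the difference is √[(0.16 + 0.16) / 4033] = 0.0089, or 0.89 percentage points. A 5% relative shift on 20% is 1.0 point, a little over one standard error. A 2% shift is 0.4 points, under half of one.

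**Step 3. Apply assumed shifts.** The documents give no recording shift. The values of s below are assumptions: the relative change in recorded PIP, averaged over the whole intervention arm, with prescribing unaffected.

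| Assumed shift s | No true effect, rate 0.20 × (1 ± s): significant result (up / down) | True 15% reduction, rate 0.17 × (1 + s) | Power |
|---|---|---|---|
| 0 | 5% | 0.1700 | 93.5% |
| 2% | 7.3% / 7.4% | 0.1734 | 86.6% |
| 5% | 19.9% / 20.5% | 0.1785 | 69.3% |
| 10% | 59.7% / 62.9% | 0.1870 | 31.5% |

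An upward shift of 1 / 0.85 − 1 = 17.6% would mask the planned effect completely.

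**Step 4. What these figures leave out.**
- The z test stands in for the planned random-effects Poisson model and ignores baseline adjustment. Adjustment would shrink the standard error, so a given shift would produce more false positives than the table shows.
- The shift is an arm average. If only half of intervention practices changed their recording, equally weighted, an average of 5% would need 5% / 0.5 = 10% in those practices.

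**The case against.** The strongest case on the other side is that the link from the template to the outcome is inferred.

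- **Diagnosis coding.** The only example of coding in section 10.4.1 is a marker that the toolkit was used, and that section concerns fidelity. Nowhere does the protocol say that the template records diagnoses or indications. This stands. A reader might infer that ascertainment differs between arms by design; the text supports only that it may.
- **Usual care.** The PIP indicators shown on the template are ones "which have been developed for and are widely used within routine general practice", and section 9.0 describes varying template use in usual care. This stands too. What is exclusive to the intervention arm is the BRISMED template, not on-screen indicators as such. Prescribing that changes because an indicator was seen is a genuine effect of the intervention.
- **Drug records.** A reader might infer that removing unused drugs from repeat lists would lower recorded PIP. The protocol does not say that exposure comes from repeat lists; for baseline it refers to prescribing records. The concern therefore rests mainly on disease codes.
- **Size.** The indicator definitions are not given, so the share that depends on disease codes is unknown. The shifts are assumed, opposing shifts could partly cancel, and section 5.2.1 accepts that not all intervention practices may engage fully. All of this limits the size, not the mechanism.
- **Detail for the SAP.** Code lists and look-back windows belong there, and the SAP may contain a check. But the protocol itself gives the reassurance, and it does so without considering whether recording is equal between arms.

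**Conclusion.** The point holds as a gap in the protocol's reasoning about missing data, with a cheap safeguard available. Section 11.3.3 relies on an assumption that is safe for the treatment comparison only under similar recording in both arms. A recording tool goes to one arm, and baseline adjustment cannot correct a change that starts after randomisation. Whether recording will change, by how much and in which direction cannot be learned from the documents.

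The figures are therefore illustrative. Under the plan's inputs, an assumed arm-wide shift of 2% has little effect on the false-positive rate (about 7%). At 5% it is about 20%, and at 10% it is 60–63%. In the masking direction, power is about 87%, 69% and 31.5%.

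Two stronger readings are not supported. The sample size calculation is not in error, since its power reproduces. Nor do the documents justify redefining the primary outcome, or making a claim of benefit conditional on a second significant result: the first would remove PIP linked to newly recorded conditions from the main estimate, and the second would add a hurdle whose cost in power has not been worked out.

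**What to change.** Keep the primary outcome and primary model as they are, and make three changes.

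1. **Section 11.3.2:** add a pre-specified sensitivity analysis that re-derives 12-month PIP in both arms, with the disease conditions in each indicator taken only from codes dated before randomisation and drug exposure taken from prescribing records at 12 months. Report it beside the primary estimate.
2. **Reporting:** give, by arm, the rate of diagnosis codes newly added or ended during the intervention year.
3. **Section 11.3.3:** qualify the statement on missing data to say that, for the comparison between arms, it requires similar recording in both.

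The cost is wording and one further run of the PIP algorithm. Baseline PIP already has to be derived from pre-randomisation records, so the step should be feasible. It does need dated diagnosis codes in the ORCHID processing, so it should be specified before the data minimisation described in section 13.2. The drawback is that the sensitivity analysis does not count PIP tied to conditions first recorded during the year, in either arm. A difference from the primary result therefore calls for interpretation alongside the by-arm coding rates and does not by itself prove a recording artefact.

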#### 12.0 Economic evaluation

#### 12.1 Health economic cost consequence analysis

There is a paucity of robust economic evidence on medication reviews; one review study found few trials had included an economic evaluation and those that did were of limited quality[47]. Good economic evidence is crucial to determine if the time, effort and costs involved in conducting a medication review using the BRISMED Toolkit are an appropriate use of limited NHS resources.

The outcomes from improved medications reviews are multiple and include health and non-health benefits which are difficult to reduce to a single measure. In this trial the economic evaluation will be a cost consequence analysis (CCA)[48] which considers all the health and non-health benefits of an intervention, even those which cannot be costed. This is a distinguishing feature from other types of economic analysis. It accepts that different types of benefits cannot be measured using the same units and reports them in a disaggregated form. The initial cost of implementation is compared to subsequent NHS savings and changes in patient reported outcomes. This will provide a table of mean costs and outcomes/effects with incremental differences between the trial arms, including confidence intervals and p values. A CCA will provide a clear descriptive summary that will allow decision makers to form their own opinion on the importance and relevance of the costs and outcomes to their decision-making context. CCAs have been recommended for interventions (such as BRISMED) that have multiple effects[49], and a combination of numerous health and non-health benefits that may be difficult to measure in a common unit[50].

We will record direct costs to the NHS of implementing the BRISMED Toolkit (engagement events, materials, training, staff time to deliver intervention, etc.) as well as indirect (productivity losses, additional GP consultations, unplanned admissions) and intangible costs (quality of life, patient experience). Routine data will allow us to compare costs of long-term medicines and subsequent care use (i.e. GP consultations, admissions, ED visits) between arms. Using CCA will allow us to report other relevant outcome information collected in a subset of patients including duration of medication reviews (audio recordings in 300 patients), and patient experience and quality of life (patient surveys). EQ-5D is the most widely used measure of quality of life, although it is unclear whether it will be sensitive to the effect of medication reviews. We will, however, include EQ-VAS which was found by the DREAMeR study to be impacted by medication review[36].

The approach for dealing with missing data or response bias will reflect that taken for the other statistical analyses mentioned earlier.

In the present study it is not possible to use longer-term economic modelling, firstly as medication reviews will occur multiple times (at least annually) there is a (complex and unpredictable) accumulative effect to consider which would require a longer period of observation. Secondly there is no cost effectiveness outcome in the current study such as an incremental cost effectiveness ratio or net monetary benefit. The reasons for not pursuing a cost effectiveness analysis are three-fold: firstly, in the short-term we are unlikely to see a change in quality of life measures, and therefore we could not justify the additional cost of collecting them beyond baseline; secondly, a cost effective outcome based on cost per incidence of PIP avoided is not a very useful measure for decision makers; thirdly, the intervention involves multiple effects and a combination of health and non-health benefits which are difficult to combine into one single measure. In these cases, the recommended analysis is cost consequences, which is what we are pursuing.

The health economic analyses will follow a pre-defined detailed approach presented in a separate Health Economics Analysis Plan (HEAP).

#### 13.0 Data handling

#### 13.1 Data collection tools

Data for the main analysis will be collected through the ORCHID network. This includes a database of contact details for individual practices participating in ORCHID. The ORCHID database is hosted by the Nuffield Department of Primary Care Health Sciences at the University of Oxford. The network is a resource for UK-wide health research and a Trusted Research Environment (TRE) with expertly curated themed datasets to support health research. The pseudonymised data, extracted by information service providers, are processed within the private and secure network of the Clinical Informatics and Health Outcomes Research Group at University of Oxford under a formal data sharing agreement.

For the purposes of the process evaluation, patient and practice staff contact details in the 56 participating practices needed for day-to-day study management will be entered onto the trial management REDCap database. Other quantitative process evaluation data will primarily be in the form of participant self-report of online questionnaires. These data will be anonymised and entered directly into a REDCap database, held on secure servers at the University of Bristol; equivalent online forms will be developed within REDCap itself. REDCap is a secure web application for building and managing online surveys and databases. REDCap is specifically geared to support online or offline data capture for research studies and operations. The REDCap Consortium, a vast support network of collaborators, is composed of thousands of active institutional partners in over one hundred countries who utilise and support REDCap.

Further data for the qualitative elements of the process evaluation will be collected by the qualitative researcher using a variety of media as detailed elsewhere. Audio recordings will be captured using encrypted recording software/hardware. Transcriptions will be undertaken by a service approved by University of Bristol and transferred in an anonymised format to the institution's secure Research Data Storage Facility (RDSF) for analysis.

#### 13.2 Data handling and record keeping

Anonymous data extracted for the main analysis (including any externally linked data, such as hospital records) will be initially stored and processed within the University of Oxford's systems, in line with standard ORCHID processes. Only once processed, with required data minimisation applied, will any data be transferred to the University of Bristol RDSF for statistical analysis. These data will only be labelled with anonymous identifiers, and will not identify patient, practice or PCN.

Four separate servers will be used to store the main trial analysis data (RDSF), survey data (REDCap), qualitative recordings (RDSF), and any person-identifiable data (REDCap trial management database).

Data will be collected and retained in accordance with the General Data Protection Regulation 2018 (GDPR) (see section 17.6 Data protection and patient confidentiality for more details) and The University of Bristol, Research Data Service 'Guidance on the Retention of Research Records and Data' (Version 2.0 January 2019) .

In accordance with REC requirements, regulatory authorities including monitors and auditors from NHS Trusts may request access to source data and documents for cross checking. This will be

explained in the participant information sheet and a statement included as part of the written consent form to be signed by the participant.

## 13.3 Access to data

The Senior IT Manager (in collaboration with the trial manager and Chief Investigator) will manage access rights both to the participant contact data in the trial management REDCap database, to the survey data held in REDCap, and to the main trial analysis data and qualitative data stored in the respective RDSF servers.

Prospective new users must demonstrate compliance with legal, data protection and ethical guidelines before any data are released. We anticipate that once the trial is completed, anonymised trial data will be made available through the RDSF to facilitate sharing with other researchers once appropriate (separate) approvals are in place.

